#### **CKD-EPI Stage 3a (eGFR 45 mL/min/1.73 m^2 to <60 mL/min/1.73 m^2)**

6 mL of solution from a single vial (corresponding to neridronic acid 75 mg) will be diluted in 500 mL normal saline and administered by slow intravenous infusion (240 minutes [maximum 260 minutes]) at each treatment visit, resulting in a total dose of 300 mg neridronic acid or matching placebo.

#### **CKD-EPI Stage 3b (eGFR 30 mL/min/1.73 m^2 to <45 mL/min/1.73 m^2)**

5 mL of solution from a single vial (corresponding to neridronic acid 62.5 mg) will be diluted in 500 mL normal saline and administered by slow intravenous infusion (240 minutes [maximum 260 minutes]) at each treatment visit, resulting in a total dose of 250 mg neridronic acid or matching placebo.

For additional requirements related to the IMP infusion, please refer to Section 10.2 of the trial protocol.

#### **1.4.2 Prior/concomitant medications or therapies**

Subjects participating in the trial must be on stable therapy prescribed for CRPS, including any multidisciplinary treatment program (e.g., consisting of physical therapy, occupational therapy, cognitive behavioral therapy, and/or graded motor imagery, including mirror feedback). Initiation of a new interdisciplinary treatment program during the trial is prohibited. Other allowed therapies, such as spinal cord stimulation, may be continued during the trial if they are stable for at least 1 month prior to the start of treatment.

Subjects may continue treatment with allowed concomitant medications, including any stable analgesic regimens consisting of opioids and other analgesics, if they are on a stable, well-defined treatment regimen for at least 1 month before allocation to IMP and are anticipated to be able to maintain the treatment regimen up to and including Visit 8 at a minimum in the opinion of the investigator. A prescribed regimen including an as needed dosing schedule is permitted. A subject who does not take prescription analgesics but does take over-the-counter analgesics is permitted to participate if considered stable and anticipated to be able to continue taking only over-the-counter and non-prescription analgesics up to and including Visit 8 at a minimum. Over-the-counter analgesics must remain stable throughout the trial, up to and including Visit 8 at a minimum. After Visit 10, investigators should assess the further need of concomitant treatment for CRPS, in particular opioids, and evaluate if the dose or frequency of these treatments can be decreased, or if treatment can be stopped completely. Any resulting changes must be documented in the electronic case report form (eCRF). Subjects receiving treatment in Treatment Period B should remain on stable analgesic treatment (including over-the counter analgesics) between Visit 11 and Visit 16.

In the event a subject experiences a severe pain flare related to CRPS, trauma, or other reason, a course of short-acting analgesics, including opioids, may be prescribed for up to 2 weeks. The concomitant medication must be documented in the eCRF and the sponsor or sponsor's representative (i.e., medical monitor) must be notified.

To alleviate the expected flu-like symptoms (acute phase reaction) potentially associated with the first intravenous administration of bisphosphonates, all subjects in both treatment groups must receive oral acetaminophen (paracetamol) starting from approximately 1 hour prior to the first infusion of IMP and then approximately every 6 hours for the 72-hour period after the first infusion in Treatment Period A and Treatment Period B. Commercially available doses of acetaminophen (paracetamol) can be used as available in the country where the trial is performed. However, the total dose of acetaminophen, including any other medications that contain acetaminophen, must not exceed the maximum allowed dose according to the local product information, and not more than 4 g/day, due to acetaminophen's known risks for hepatic toxicity. Non-steroidal anti-inflammatory drugs should not be used to alleviate the symptoms of the acute phase reaction due to their potential to cause acute changes in renal function, which may confound renal safety assessments.

All subjects will be provided with supplemental calcium and vitamin D, starting from Visit 1 and continuing through to the end of the trial. Calcium and vitamin D supplementation are considered standard of care for patients treated with bisphosphonates and other drugs that inhibit bone turnover. An appropriate daily supplement should be provided to subjects (recommended doses are 500 mg/day to 1000 mg/day calcium and approximately 1000 IU/day vitamin D as locally authorized); if a subject is currently taking calcium and vitamin D supplements, these may be continued without need for additional supplementation, provided levels of supplementation are

similar to those recommended above. A combination product of calcium and vitamin D may be used. Subjects with vitamin D below 30 ng/mL (75 nmol/L) should receive higher doses of vitamin D during the Enrollment Period (e.g., 10 000 IU/day for 10 days), to meet the protocol-required vitamin D levels prior to starting treatment at Visit 2 and prior to starting treatment at Visit 11. As repletion of vitamin D to these levels can be difficult, repeated laboratory testing for vitamin D is permitted during the Enrollment Period (up to a maximum of 4 times in 60 days) and between Visit 10 and Visit 11 (up to a maximum of 2 times). High doses of vitamin D should not be continued after the subject reaches vitamin D targets (supplementation should continue at the recommended daily dose of approximately 1000 IU/day).

With regard to the calcium and vitamin D supplements, the investigator should promote compliance by instructing the subject to take the supplements as prescribed and by stating that compliance is necessary for the subject's safety. Subjects should be instructed to contact the investigator if they are unable for any reason to take the supplements as prescribed. When used as daily supplements in this trial, calcium and vitamin D are not to be considered as an IMP or a medical treatment for an adverse event.

#### **1.4.2.1        Forbidden concomitant medications**

The following medications are forbidden for the duration of the trial or as specified:

- Any experimental or investigational treatment or therapy.
- High-dose opioid analgesics (greater than 200 mg oral morphine equivalent daily dose) or combinations of opioids and benzodiazepines or any other treatment regimens that may have potential for significant opioid/sedatives side effects and that may be considered unstable or unsafe (according to the judgment of the investigator).
- Concomitant use of drugs with the potential to cause hypocalcemia (e.g., aminoglycosides). Subjects on a stable dose of loop diuretics may be allocated to IMP as long as no dosage increases in the diuretic medication are anticipated and calcium levels are in the reference range.
- Oral, intravenous, or intramuscular bisphosphonates, calcitonin, denosumab, anti-angiogenic drugs or other bone-active drugs (e.g., teriparatide).
- Drugs with risk for torsades de pointes as specified:
  - Drugs with a known risk of torsades de pointes within 7 days prior to allocation and throughout the trial.
  - With the following exceptions: selective serotonin re-uptake inhibitor antidepressants (e.g., citalopram, escitalopram), if QT interval values met entry criteria, subjects were on a stable dose for at least 1 month prior to Visit 1, and doses are expected to stay stable throughout the trial.
- Concomitant administration of non-steroidal anti-inflammatory drugs or any other agents with the potential to interfere with the assessment of potential changes in renal function (e.g., angiotensin converting enzyme inhibitors) until 2 weeks after the last IMP administration per treatment period, unless subjects are receiving a stable dose for at least 1 month prior to Visit 1. Non-steroidal anti-inflammatory drugs should not be used to alleviate the symptoms of the acute phase reaction.

- Use of nerve blocks, ketamine infusions, intravenous immunoglobulin, acupuncture, electromagnetic field treatment, initiation/implementation of radiofrequency ablation or other sympathectomy procedures, or peripheral nerve stimulation, within 6 weeks prior to Visit 1 and for the entire duration of the trial.
- Use of systemic steroids starting 2 weeks prior to Visit 1 and for the entire duration of the trial.

## 1.5 Statistical analyses

The primary analysis will be performed once all subjects have completed Visit 11 (Week 26), including database lock and unblinding. The results from this 26-week analysis will be reported in an interim integrated clinical trial report.

The final analysis of this trial, including Treatment Period B and Follow-up Period 2, will be performed after the last subject has completed the trial and the database has been locked.

### 1.5.1 Sample size rationale

The sample size is based on a statistical test of the superiority of 400 mg neridronic acid versus placebo in the primary endpoint. The null hypothesis of no effect,  $H_0: 0 \leq \mu_{400} - \mu_0$ , is tested against the alternative hypothesis  $H_1: \mu_{400} - \mu_0 < 0$ . (Note: A pain reduction will be analyzed as a negative change from baseline. An effective treatment will lead to reduced pain and, hence, to a negative mean change from baseline,  $\mu < 0$ ).

For a difference in the means of  $\mu_{400} - \mu_0 = -1.0$  points on the NRS, assuming a standard deviation of 2.0 points on the NRS and a 1-sided significance level of 2.5% ( $\alpha = 0.025$ ), 86 subjects per arm will be required to provide at least 90% power ( $1-\beta = 0.9$ ) to reject the null hypothesis. To compensate for a slight decrease in power due to an optional futility interim analysis, a total of 180 subjects (90 subjects per arm) are planned to be allocated to treatment.

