#### 1.5.3.7 Interim analysis

An interim analysis is planned after a combined total of approximately 80 subjects in the two Phase III trials, KF7013-02 and KF7013-04, have completed Week 12 of treatment and the required data is available in the databases. The interim analysis is for futility only and will be non-binding. The futility criterion will be based on the unblinded comparison of the primary endpoint and will be calculated using identical methods as for the final analysis. If the observed difference in the means of  $\mu_{400} - \mu_0$  is  $\geq -0.3$  points on the NRS, the null hypothesis will not be rejected and the recommendation will be to stop both trials. The interim analysis will be performed by an independent statistical analysis unit not otherwise involved in the conduct of the trial and the result will only state the recommendation to stop or continue the Phase III program. No unblinded information will be disseminated to the trial teams. Pending recruitment rates of both trials, it may

be decided to forgo the interim analysis or conduct it at a different point in time. As the interim analysis will be for futility only, no inflation of the type I error will occur.

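### The 4 extra subjects per arm do not compensate for the futility look: if it is held at about 80 pooled subjects and followed, 90 per arm gives about 87% power, not 90%

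*Protocol*

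**What the plan says.** Section 1.5.1 (Sample size rationale) assumes a mean difference of -1.0 NRS points, a standard deviation of 2.0 and a one-sided level of 2.5%. It states that "86 subjects per arm will be required to provide at least 90% power". It then gives one reason for planning more than that: "To compensate for a slight decrease in power due to an optional futility interim analysis, a total of 180 subjects (90 subjects per arm"). No power figure is given for the design with the look included.

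Section 1.5.3.7 (Interim analysis) fixes the look: "An interim analysis is planned after a combined total of approximately 80 subjects in the two Phase III trials" have completed Week 12. If the observed difference is at or above -0.3 "points on the NRS, the null hypothesis will not be rejected and the recommendation will be to stop both trials". The same section says "The interim analysis is for futility only and will be non-binding", and that, depending on recruitment, it may "be decided to forgo the interim analysis or conduct it at a different point in time".

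**The concern.** Section 1.5.1 presents the power cost of the look as slight and already covered by 4 more subjects per arm. The look comes early, with about 40 per arm pooled, and its cutoff of -0.3 is only 0.7 points from the planning effect. The interim difference is imprecise at that size, so a working drug has a real chance of landing on the wrong side of the cutoff. Those who decide whether to hold, time or follow the look would be relying on a statement that the cost has been met. If it has not, following the look leaves the probability of success below the 90% used to size the trial. Type I error, the estimand and subject safety are not involved.

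**Working it through.** **Inputs**
- Difference -1.0, SD 2.0, one-sided alpha 0.025, 86 then 90 per arm: Section 1.5.1.
- 1:1 allocation: Section 10.3.
- Look at about 80 pooled subjects (about 40 per arm), stop if the difference is -0.3 or greater: Section 1.5.3.7.
- Not stated: how many of the 80 come from this trial. The full range from 0% to 100% is shown.
- Assumed: the same effect and SD in both trials; the interim estimate uses the 80 Week 12 completers only; no dropout; no gain from covariate adjustment. The last two match the basis of the protocol's own 86.

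**Step 1. Reproduce the protocol's figure (no look).** Two-sample t-test power from the noncentral t, with noncentrality 1.0 / (2.0 × √(2/n)) and 2n - 2 degrees of freedom:
- n = 85: 89.99%
- n = 86: 90.3%
- n = 90: 91.6%

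So 86 per arm is correct, and 4 more per arm add about 1.2 points.

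**Step 2. Chance of a stop recommendation at the planning effect.** The standard error of the pooled interim difference is 2.0 × √(2/40) = 0.447. The cutoff lies 1.0 - 0.3 = 0.7 from the true value, so

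P(stop recommended) = 1 - Φ(0.7 / 0.447) = 5.9%, or about 1 in 17.

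**Step 3. Power when the recommendation is followed.** This is P(interim difference below -0.3 and final test significant). The interim and final differences are taken as bivariate normal, with the t critical value for the final test. If f subjects per arm at the interim come from this trial, the correlation is f / √(40 × n). At n = 90 and f = 20 this is 20/60 = 0.33.

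| Share of the 80 from this trial | Power at 90 per arm, rule followed | Simulation with t-tests |
|---|---|---|
| 0% | 86.2% | 86.1% |
| 25% | 86.6% | 86.5% |
| 50% | 87.1% | 87.0% |
| 75% | 87.7% | 87.7% |
| 100% | 88.5% | 88.4% |

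Using the normal critical value instead of t raises these slightly (86.4% to 88.7%) and changes nothing.

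**Step 4. Compare loss and compensation (even split).**
- Loss at 90 per arm: 91.6 - 87.1 = about 4.5 points.
- With 86 per arm and the rule followed, power is 86.0%. The 4 extra per arm therefore recover 87.1 - 86.0 = about 1.1 points.

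**Step 5. What would restore 90%.** At an even split and the planned timing, about 105 per arm. Alternatively, keeping 90 per arm, a look at about 130 pooled subjects (90.1%; at 120 it is 89.7%).

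**The case against.** Four points deserve weight.

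1. **The loss is conditional.** The look is optional, non-binding and movable. If it is skipped or overridden, 90 per arm gives 91.6%, above target. This is true, but in that case there is no loss to compensate. The sentence in Section 1.5.1 concerns the case where the look is held and followed, and there it fails at the planned timing.

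2. **The interim estimate may be more precise than 40 completers per arm.** Section 1.5.3.7 calls for the same method as the final analysis, an MMRM over Weeks 1 to 12, and subjects still in follow-up might contribute. If that were worth 50 per arm, power would be 88.7% at an even split and 90.1% if all came from this trial; at 65 per arm it would be 90.1% at an even split. This stands as a limit on the figures: 86% to 88.5% applies to a completers-only look. The protocol gives neither the number of ongoing subjects nor the correlation between weeks, so the gain cannot be claimed.

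3. **Baseline adjustment could reduce the residual SD.** At 1.9 instead of 2.0, power with the rule followed would be about 90.0% at an even split. But Section 1.5.1 takes no such credit for its 86 per arm. It also makes no allowance for dropout, which would work the other way.

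4. **The final test is not weakened.** Given that the trial continues, power is 0.871 / 0.941 = about 92.5%. The whole cost lies in wrongly stopping. That is the right way to read the loss, and it does not reduce it.

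Whether 4.5 points is slight is a matter of judgement. Whether 4 subjects per arm make up for it is not.

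**Conclusion.** The compensation claim in Section 1.5.1 is wrong as written. The 86 per arm is correct; the fault lies only in the allowance for the look. With the look at about 80 pooled completers and its recommendation followed, power at 90 per arm is about 87%, some 3 points below the 90% used to size the trial. It is below 90% for every possible split of the 80 between the two trials. The result rests on equal effect and SD in both trials, a single pooled difference as the stopping criterion, and a completers-only interim estimate. It does not apply if the look is forgone, overridden or held much later. The statement should be corrected, but no analysis or error rate depends on it.

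**What to change.** In Section 1.5.1, replace the compensation sentence with the conditional figures, for example:

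> *A total of 180 subjects (90 per arm) are planned. Power is about 91.6% if the futility look is forgone or its recommendation is not followed. It is about 87% (86% to 88.5%, depending on the share of interim subjects from this trial) if the look is held at about 80 pooled subjects and followed. The latter figures count Week 12 completers only.*

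If the sponsor intends to include subjects still in follow-up at the interim, it should state that and give the power on that basis. The figures should be recomputed if the timing of the look changes.

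The cost is one sentence. Sample size, cutoff and timing need not change. The price is a less favourable stated power for the case where the look is followed.

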### 1.5.2 Subject populations

**Enrolled Set:** The Enrolled Set includes all subjects who signed the informed consent form.

**Allocated Set:** The Allocated Set includes all subjects who are allocated to treatment.

**Safety Set:** All subjects with at least 1 IMP administration, including any partial infusion.

**Full Analysis Set:** All subjects allocated with at least 1 IMP administration, including any partial infusion.

**Pharmacodynamic Set:** All treated subjects with at least 1 non-missing value for at least 1 of the bone turnover markers.

### 1.5.3 Statistical methods and analysis

The analysis of primary and secondary efficacy endpoints is described in the subsections below. All other efficacy endpoints will be descriptively summarized in the Full Analysis Set. Confirmatory testing will be performed for the primary endpoint and for selected secondary endpoints. Further

analyses may be done, including statistical hypothesis tests, but all analyses will be exploratory in nature and will not provide confirmatory evidence.

Subject disposition as well as demographic and baseline data and other subject characteristics, e.g., medical history and prior and concomitant medications, will be descriptively summarized for the Full Analysis Set and the Safety Set.

Adverse events, laboratory values, ECG, vital signs, and further safety parameters will be summarized descriptively for the Safety Set. All laboratory parameters will be collected both in SI units and US conventional units. All parameters will be reported in SI units and, in addition, selected laboratory parameters will be reported also in US conventional units (dual reporting).

Bone turnover marker values will be descriptively summarized by parameter for the Pharmacodynamic Set.

Health economics and work productivity data will be summarized descriptively for the Full Analysis Set.

Analysis of sIL-2R concentrations will be summarized descriptively for the Safety Set.

All efficacy and safety data evaluated during Treatment Period B and Follow-up Period 2 will be analyzed descriptively separately for subjects who are treated in Treatment Period B and subjects who are not treated. For subjects treated in Treatment Period B, analyses will be performed for subjects initially treated with placebo and subjects initially treated with neridronic acid.

### **1.5.3.1 Primary endpoint**

See Section 1.2 for the definition of the primary endpoint.

For the primary objective of the trial, the primary estimand is the difference in means of the primary efficacy endpoint of 400 mg intravenous neridronic acid compared to placebo for all allocated and treated subjects. This treatment policy or *de facto* estimand measures the effect of neridronic acid regardless of adherence to treatment or protocol.

The primary estimand will be estimated by the analysis of the primary efficacy endpoint for the Full Analysis Set. The primary analysis will fit a mixed model for repeated measures (MMRM) to the change from baseline in the average pain intensity scores from Week 1 to Week 12 recorded once daily in the electronic diary, including the covariate baseline pain intensity score, and the factors geographic region, week, treatment, and treatment-by-week interaction as fixed effects, and an unstructured covariance matrix to model the covariance structure of the repeated measurements.

The primary efficacy analysis will be performed using the contrast, i.e., the mixed model Wald test, of neridronic acid 400 mg versus placebo at Week 12 of the treatment, week and treatment-by-week interaction term of the mixed effects model described above. Model-based parameter estimates, standard errors, 95% confidence intervals, and p-values will be tabulated. This analysis will be performed using only the observed values without imputation of missing values.

Additional sensitivity analyses will be performed to assess the robustness of primary analysis results. Sensitivity analyses will include the imputation of missing pain intensity scores using different pattern mixture models (PMMs).

A descriptive summary of the weekly averages and the changes from baseline will be generated by treatment group. Graphical displays will be used if appropriate.

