### **8.1.1 Rationale for the trial population**

Although previous trials with neridronic acid have been performed in subjects with CRPS-I, CRPS-I and CRPS Type II (CRPS-II) are likely to share the same pathophysiological basis (Oaklander and Horowitz 2015; Bruehl 2015).

There are no known methods to objectively distinguish between CRPS-I and CRPS-II subtypes, as electromyography and nerve conduction studies have low negative predictive value and do not rule out nerve abnormalities in CRPS-I. Furthermore, pathophysiological changes in bone, the principal target for efficacy of neridronic acid, may occur in patients diagnosed with CRPS-II.

Given the uncertain distinctions between these subtypes and lack of pathologic or pharmacologic basis for restricting treatment to CRPS-I, subjects with CRPS-II will also be included in this trial.

Reports from the literature suggest better responses to treatment when subjects are treated early after onset of the first symptoms (Wertli et al. 2014). There is no consensus on an exact time window for treatment. Preliminary data from an open-label trial employing a cumulative dose of neridronic acid 400 mg (KF7013-03), suggest clinically relevant decreases in pain intensity in a subgroup of subjects with a CRPS duration  $\leq$  2 years. The trial population in this trial will therefore be limited to this disease duration.

Subjects must be on stable therapy prescribed for CRPS for at least 1 month prior to randomization and allocation to maximize sensitivity to detect changes in pain intensity and other efficacy outcomes. Analgesic regimens including pro re nata (as needed) opioids or other analgesics are allowed if the regimen has been prescribed as part of a stable treatment. The investigator must select subjects who are anticipated to be able to maintain a stable treatment regimen for the first 12 weeks of the trial (up to and including Visit 8). Initiation of new therapies during the trial will be prohibited. Short courses of analgesics, including opioids (unless prohibited according to Section 1.4.2.1), will be allowed to be prescribed in the event of a severe pain flare.

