## **10.3        Method of assigning subjects to treatment (allocation)**

On Day 1, subjects who comply with all inclusion criteria and do not meet any of the exclusion criteria will be randomly allocated to 1 of the 2 treatment groups in a 1:1 ratio stratified by geographic region. Treatment assignment will be performed centrally using an interactive response technology system prior to the first intravenous infusion of IMP. The details of the vendor and system will be filed in the trial master file.

The investigator (or delegate) must log into the system using their own user identification number and a password. The investigator (or delegate) will enter the subject's number and other information required by the system to obtain a medication number. The medication number will then be used to select the correct package of IMP to give to the subject.

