  - Sudomotor/edema: evidence of edema and/or sweating changes and/or sweating asymmetry.
  - Motor/trophic: evidence of decreased range of motion and/or motor dysfunction (weakness, tremor, dystonia) and/or trophic changes (hair, nail, skin).
4. There is no other diagnosis that better explains the signs and symptoms.

IASP = International Association for the Study of Pain.

Source: Harden et al. 2010a

In accordance with procedures for validation of these criteria, symptoms will be assessed with a recall period “since the onset of CRPS”. Signs must be present, i.e., observed by the examiner, during the evaluation at the Enrollment Visit. Subjects will be examined for 8 signs (observed on examination, yes or no): hyperalgesia to pinprick; allodynia (light touch, deep joint pressure, vibration, cold, and heat); temperature asymmetry by palpation (affected side cooler or warmer than the contralateral side); skin color asymmetry (red, blue or pale, mottled, or scar); asymmetric edema; sweating asymmetry (increased or decreased on the affected side); dystrophic changes (nails, hair, or skin); and motor changes (tremor, dystonia, decreased AROM, or weakness).

Medical history related to CRPS must include the following: date and description of precipitating event (e.g., type of trauma, surgery [including any information on whether there was a major nerve injury]; if no precipitating event is known, document as unknown), the specific location of CRPS, including the affected limb (if more than 1 limb is affected, the most painful limb as well as any other affected limb must be identified), the date of onset of symptoms, the date of CRPS diagnosis, and the type of CRPS (CRPS-I or CRPS-II). Any documentation supporting the diagnosis of CRPS, including any assessments used to rule out alternative diagnoses, will be retained.

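### CRPS duration, on which the protocol restricts entry and which it records for every subject, is neither a stratification factor nor a covariate in the primary model: a modest missed gain in precision

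*Protocol*

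**What the plan says.** **Model.** Section 1.5.3.1 fits an MMRM to the weekly change in diary pain from Week 1 to Week 12, "including the covariate baseline pain intensity score, and the factors geographic region, week, treatment, and treatment-by-week interaction as fixed effects", with an unstructured covariance matrix. Section 14.1.7.1.1 repeats the list. The protocol therefore sets the covariates itself.

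**Allocation.** Section 10.3 randomises "in a 1:1 ratio stratified by geographic region". No other stratum is named.

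**Duration and response.** Section 8.1.1 states: "Reports from the literature suggest better responses to treatment when subjects are treated early after onset of the first symptoms". It adds that no time window has been agreed, and that preliminary open-label data "suggest clinically relevant decreases in pain intensity in a subgroup of subjects with a CRPS duration" of 2 years or less. It gives this as the reason for limiting the population to that duration, and inclusion criterion 3 (Section 1.3.1) applies the limit.

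**Availability.** Section 12.2.3.1 requires the CRPS history to include "the date of onset of symptoms, the date of CRPS diagnosis". Section 1.6.1 (footnote f) lists the onset date within the history taken at Visit 1.

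**Size.** Section 1.5.1 assumes a difference of 1.0 NRS point, an SD of 2.0 and a one-sided 2.5% level. It concludes that "86 subjects per arm will be required to provide at least 90% power", and then that "a total of 180 subjects (90 subjects per arm) are planned to be allocated to treatment".

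**The concern.** The sponsor found the evidence on duration strong enough to shape the entry criteria, and then did not use the variable at allocation or in the primary analysis. Criterion 3 sets an upper limit on duration but no lower one, so variation remains among enrolled subjects. If duration predicts the Week 12 change within that range, the part not already explained by baseline pain and region stays in the residual error. A chance difference in duration between the arms would then also move the Week 12 contrast in that particular trial, in either direction.

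At stake is a little power in a trial whose step from 86 to 90 per arm is attributed to the futility look, with no dropout allowance stated. Timing also matters. Section 1.5.3 classes further analyses as exploratory, so an adjustment chosen after unblinding would carry no confirmatory weight.

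**Working it through.** **Inputs from the protocol (Section 1.5.1).** Difference 1.0, SD 2.0, one-sided alpha 0.025, target power 90%, 86 per arm required, 90 per arm planned.

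**Assumed input.** The documents give no figure for r, the correlation of duration with the Week 12 change after baseline pain and region. The range 0.1 to 0.3 is an assumption.

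**1. The protocol's own figure.** Two-sample t-test, noncentral t with noncentrality 1.0 / (2.0 × √(2/n)) and 2n − 2 degrees of freedom. Power is 89.99% at n = 85 and 90.3% at n = 86, so 86 per arm reproduces. At the planned 90 per arm, SE = 2.0 × √(2/90) = 0.298 and power is 91.6%. This assumes complete data and no futility look.

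**2. With duration as a covariate.** Residual SD = 2.0 × √(1 − r²). The unadjusted sample size giving the same precision is 90 / (1 − r²).

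| r | Residual SD | SE at 90 per arm | Power | Equivalent n per arm |
|---|---|---|---|---|
| 0 | 2.000 | 0.298 | 91.6% | 90 |
| 0.1 | 1.990 | 0.297 | 91.8% | 90.9 |
| 0.2 | 1.960 | 0.292 | 92.6% | 93.8 |
| 0.3 | 1.908 | 0.284 | 93.8% | 98.9 |

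The gain is 0.2 to 2.2 percentage points of power, worth about 1 to 9 subjects per arm. The degree of freedom spent on the term changes these powers by about 0.01 of a percentage point.

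**3. If duration acts in the active arm only.** Section 8.1.1 speaks of response to treatment, so this case is plausible. Let the active-arm correlation be r, the placebo-arm correlation zero and the SD 2.0 in both arms. A common slope is then half the active-arm slope. The residual variance is

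- active: 4 × (1 − r² + r²/4) = 4 × (1 − 0.75r²)
- placebo: 4 × (1 + 0.25r²)
- average: 4 × (1 − 0.25r²)

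The effective correlation is therefore r/2. For r = 0.1 to 0.3 it is 0.05 to 0.15, and power is 91.6% to 92.1%.

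**4. Chance imbalance.** The standardised difference in mean duration between arms has SD √(2/90) = 0.149. It exceeds 0.2 in absolute value with probability 2 × (1 − Φ(0.2/0.149)) = 18%. With a common slope, an imbalance of 0.2 SD shifts the unadjusted estimate by r × 2.0 × 0.2, which is 0.04 points at r = 0.1 and 0.12 points at r = 0.3. The latter is 0.12 / 0.298 = 0.4 of a standard error. The imbalance is as likely to favour the drug as to disfavour it.

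**The case against.** The strongest reply is that nothing here is an error. The model adjusts for the baseline value of the outcome and for the only stratification factor, which is a coherent prespecified choice, and the trial passes its 90% target without duration. That stands: no stated figure changes.

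Three stronger readings are tempting, and the documents support none of them.

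- A reader might infer that the protocol identifies duration as an established driver of response. Section 8.1.1 only reports that the literature and preliminary open-label data suggest a link, and it gives no gradient within the first 2 years. It concerns response to treatment, which may be effect modification rather than prognosis in both arms. A main-effect term then gains less, as step 3 shows.
- A reader might infer that the planned estimate is biased. Randomisation keeps it unbiased on average, and chance imbalance is already covered by its standard error and the 2.5% error rate.
- A reader might infer that the loss of precision is known. It rests entirely on an assumed correlation. The 2-year limit narrows the range of duration. Section 12.2.3 does not require copies of treating physicians' records, so onset dates may rest on recall. Both could weaken the correlation.

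It can also be said that a duration subgroup or an adjusted sensitivity analysis may be specified in the SAP, which is not shown. That is fair, and its absence from the protocol is not criticised. The covariate list of the primary model, however, is set in the protocol. None of these objections identifies a material harm from adding the term.

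**Conclusion.** The point holds as a modest missed gain in precision. Duration motivated an entry restriction and is recorded at baseline for every subject, but it is used neither at allocation nor in the primary model. The planned analysis remains valid and the sample size calculation is correct.

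On the protocol's assumptions with 90 per arm and complete data, power would rise from 91.6% to 91.8–93.8% for an assumed residual correlation of 0.1 to 0.3 acting alike in both arms. It would be about 91.6–92.1% if that correlation exists only in the active arm, and the gain is nil if the correlation is near zero. The case for the change is that it costs almost nothing, not that the benefit is large or certain.

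**What to change.** Add CRPS duration at baseline (continuous, months from symptom onset) as a further covariate in the primary MMRM in Sections 1.5.3.1 and 14.1.7.1.1, and in the Week 26 average-pain MMRM in Sections 1.5.3.2 and 14.1.7.2. Do this before unblinding. Because Section 1.5.3.7 ties the futility comparison to the methods of the final analysis, it is best settled before that look if the look takes place.

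A log scale, and extension to the DMA, PPT and edema models, are optional; the documents support neither specifically.

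The cost is one model term and one degree of freedom, with no new data collection. The remaining drawback is possible recall error in the onset date, which would reduce the gain but not affect the validity of the comparison.
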